12.4.3 Evaluations

When evaluating AEs, the Investigator must determine if the event is serious (refer to Section 12.4.1 for criteria), assess the severity of symptoms and the relationship of the event to the study device using the following guidelines:

a. Severity

- **Mild:** Subject awareness of a sign or symptom that is easily tolerated, requires no treatment, and does not interfere with subject's daily activities.
- **Moderate:** Subject awareness of a sign or symptom which may be a low level of concern to the subject and may interfere with daily activities, but can be relieved by simple therapeutic care.
- **Severe:** A sign or symptom that interrupts the subject's daily activity and requires systemic therapy or other treatment.

b. Relationship to Study Device

- **Related:** There is at least a reasonable possibility that the AE/SAE is related to the study device. Reasonable possibility means that there is evidence to suggest a causal

relationship or association between the study device and the AE. Also referred to as an ADE.

- **Unrelated:** There is little or no reasonable possibility that the AE/SAE is related to the study device. This assessment implies that the AE/SAE has no evidence to suggest either a causal relationship or association to the study device and more likely or certain an alternative etiology exists.

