7.1 Overall Study Design and Plan Description

This will be a multicenter, controlled, randomized, monocular trial of Bausch & Lomb DVisc40 (test) OVD compared to the currently marketed Alcon VISCOAT[®] (control) OVD.

Subjects scheduled to undergo cataract surgery by phacoemulsification and implantation of a posterior chamber intraocular lens (IOL) will be screened for eligibility. Subjects will be examined preoperatively to obtain a medical history, to establish a baseline for ocular condition, including ECD, and to determine eligibility. Only one eye of each subject will be included in the study. In the event that both eyes are eligible to participate in the study, the selection of the study eye will be left to the Investigator's discretion. At the time of surgery, subjects will be randomly assigned to either of the OVD groups based upon a predetermined randomization scheme. Randomization will be by a 1:1 schema (DVisc40:VISCOAT[®]) and will be stratified by site, age group and cataract severity. A method other than stratification may be employed to balance randomization. If so, the method will be specified in the statistical analysis plan (SAP).

Postoperatively, subjects will undergo ophthalmic examinations at regular intervals per the study visit schedule (refer to [Appendix A](#)). The Investigator will provide standardized pre-, intra-, and postoperative care for all study subjects at his/her site (refer to Section 11 for additional information). A delegated examiner at each site who is masked to the randomized assignment of each subject will perform all postoperative assessments.

The VISCOAT[®] OVD was chosen as the control because the product has been used in cataract surgery for over 20 years and has a proven record for safety. In addition, VISCOAT[®] OVD is classified as a dispersive OVD as is the DVisc40 OVD.

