9.2 Postoperative Masked Examiners and Masked Roles

Each site should have at least two masked examiners to perform the post-operative measurements. It is preferred that the same masked examiner perform all post-operative measurements for an individual subject.

Subjects, masked examiners, the specular microscopy reading center employees, the Sponsor (other than the assigned unmasked contact) and the CRO, with the exception of the study monitors, will be masked to the OVD treatment received.

Masking of subjects during the surgical procedure (and during the course of the study) will be discussed during a site initiation visit by the Sponsor representative with the Principal Investigator and study staff. All surgical staff present during the cataract surgery (who are unmasked) will be instructed not to discuss the OVD treatment assignment in the presence of the subject. Intraoperative surgical staff present during the cataract surgery will further confirm their commitment to not disclosing the assigned OVD treatment assignment to a subject by signing a masking commitment form prior to the initiation of the cataract surgery. Documentation will be maintained in the site files.

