10.5 Directions for Use and Administration

The test and control OVDs will be used according to the manufacturer's directions for use document.

The test and control OVD devices (DVisc40 and VISCOAT®, respectively) will be provided in 1.0 ml and 0.75 ml syringes, respectively.

The OVD material should be carefully injected into the anterior chamber using standard aseptic technique and may be injected into the chamber prior to and/or following removal of the crystalline lens. Instillation of the solution at these points is significant, in that a coating of OVD may protect the corneal endothelium from possible damage arising from surgical instrumentation or procedures during the cataract extraction surgery. The OVD may also be used to coat the tips of surgical instruments and/or an IOL prior to implantation. For example, the internal surfaces of an IOL inserter are typically filled and/or coated with the OVD to provide lubricity during IOL compression and delivery into the eye. Additional OVD, of the same product, may be injected into the anterior chamber of the eye to fully maintain the chamber or replace any volume lost during the surgical procedure.

At the end of the surgical procedure, it is recommended that the OVD material be removed from the eye as completely as practical by thoroughly irrigating and aspirating with a sterile irrigating solution.

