12.4.2 Identification and Collection

Identification and collection of adverse events (i.e. AE, SAE, ADE or UADE) begins after informed consent has been obtained and documented. Standard sources for identifying AEs include:

- Direct observation by the Investigator;
- Asking the study participant a non-specific question (e.g., “Have you had any problems since the last visit?”);
- Unsolicited volunteering of information by the study participant (e.g., “Doctor, I have had numerous headaches since I started using this lens.”); and/or

- Laboratory or test results that meet protocol requirements for classification as an AE (e.g., IOP \geq 30 mmHg).

Ocular AEs in the study eye only, ADEs, all ocular and non-ocular SAEs, and UADEs observed or elicited by the Investigator, reported by the subject, or resulting from a test result, etc., occurring during the clinical investigation must be documented. During the study, the Investigator should treat the study subject as appropriate to ensure his/her safety and welfare. Refer to Section 12.4.5 for additional information pertaining to ongoing AEs at subject exit.

Pre-existing conditions will not be considered as AEs/SAEs, but will be collected at the preoperative visit as medical history. A worsening of a pre-existing condition, with the exception of cataract in the fellow eye, during the study should be documented as an AE and evaluated accordingly.

Hospitalization is a criterion for assessment of seriousness. Hospitalizations for admission without a medical AE should be captured as a serious AE until the cause of hospitalization can be identified. However, the following reports of hospitalization without a medical AE should not be considered either serious or an AE:

- Admission for treatment of a pre-existing condition not associated with the development of a new AE or with worsening of the pre-existing condition (e.g., for work-up of persistent pretreatment lab abnormality);
- Social admission (e.g., subject has no place to sleep);
- Administrative admission (e.g., for yearly physical exam); and/or
- Optional admission not associated with a precipitation medical AE (e.g., for elective cosmetic surgery).

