Appendix C: SURGICAL PROCEDURE

All cataract surgical procedures will be performed by the same surgeon at a site, using a phacoemulsification system adjusted according to the surgeon's usual settings (power modulation should be used). In the event a different surgeon (sub-investigator) will be performing the surgical procedures, the site must request in writing sponsor's approval prior to surgery.

Intraoperative surgical staff present during the cataract surgery will confirm their commitment to not mention the treatment assignment in the presence of a subject by signing a masking commitment form prior to the initiation of the cataract surgery. This documentation will be maintained in the site files.

The surgical procedure will be performed as follows:

- The IRT system will be accessed as described in Section 9.1.2 of the protocol to identify the OVD treatment to be randomly assigned to the subject. The appropriate OVD treatment will be prepared for surgery according to the relevant DFU and made available to the Investigator.
- The eye will be prepared for surgery and draped according to the surgeon's standard procedure.
- The surgery will be performed under topical anesthesia (surgeons may use their discretion to augment with additional anesthesia).
- Adequate dilation will be obtained.
- The main incision will be made using a 1.6 – 2.8 mm keratome. This incision will be used as the main incision for the IOL implantation.
- The test or control OVD will be used to fill the anterior chamber.
- The continuous curvilinear capsulorhexis will be performed using surgeon's medical judgment and standard of care. The phacoemulsification equipment will be adjusted according to the surgeon's usual settings (power modulation should be used).
- Before IOL implantation, the anterior chamber and the capsular bag will be expanded with the test or control OVD. When the lens is in the proper position, the OVD must be completely removed.
- The incision should be checked for leaks at the end of the procedure. Wound closure should be sutureless, however, when indicated, may be sutured or glued at the discretion of the surgeon.

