- Following completion of the surgery, steroid, antibiotic, and/or NSAID drops, as per the surgeon's standard regimen, should be applied to the eye. A patch, or shield, dressing may be used at the discretion of the surgeon, if this represents their standard post-operative regimen. Additional medications (except IOP lowering drugs) as deemed necessary, may be used at the surgeon's discretion.
- The Investigator immediately at the end of each surgery will answer the following questions in writing on a subject-specific source document:
 - IOL manufacturer
 - IOL model
 - Start time of surgery (first incision)

- End time of surgery (wound closure)
- Absolute phaco time (APT) in sec
- Effective phaco time (EPT) in sec
- Phaco system manufacturer
- Use of venturi or peristaltic pump
- Flow rate (mL/min) for OVD removal with irrigation and aspiration (I/A)
- Vacuum level (mmHg) for OVD removal with I/A
- Total I/A time to remove OVD (post IOL implantation) in minutes:seconds:hundredth-of-seconds
- Incision location: cornea, limbus, sclera
- Incision size (mm)
- Estimated total volume of OVD used (approximate percent usage per syringe - e.g., 75%, 50%)
- Any intraoperative complications or deviations from usual surgical routine. Answers are to be Yes or No for the following:
 - Any device malfunctions, device use errors, or difficulty with device use (Note: Device deficiencies will be reported on a Device Deficiency Report form to the Sponsor and its representative; the original form will be stored with the site files)
 - Did the surgery need to be aborted for any reason
 - Achievement and maintenance of adequate pupil dilation
 - Complete removal of all lens material, including cortex
 - Removal of all viscoelastic from anterior chamber and capsular bag
 - Detection of any capsular tear, zonular tear or vitreous loss
 - If a suture was placed to seal the corneal incision
 - Use of your standard of care surgical medications without any prophylactic IOP-lowering treatments
 - If intracameral antibiotics were used
 - Any other intraoperative complication (if yes, specify)

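### Postoperative AE severity and device-relatedness are rated by an Investigator who is in practice the unmasked surgeon, although Section 7.1 assigns postoperative assessments to a masked examiner

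*Combined protocol and SAP*

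**What the plan says.** On who assesses after surgery, Section 7.1 states: "A delegated examiner at each site who is masked to the randomized assignment of each subject will perform all postoperative assessments". Section 11.1.3 refers to Appendix A for the content of the postoperative visits, and Appendix A marks Adverse Events at all five.

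On who handles AEs, Section 12.4.2 requires documentation of events "observed or elicited by the Investigator, reported by the subject, or resulting from a test result". Section 12.4.3 then says "the Investigator must determine if the event is serious (refer to Section 12.4.1 for criteria), assess the severity of symptoms and the relationship" to the device. An event called related is an ADE.

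On who is masked, Section 9.2 names "Subjects, masked examiners, the specular microscopy reading center employees, the Sponsor (other than the assigned unmasked contact) and the CRO", study monitors excepted. The Investigator is not named. The same section says: "All surgical staff present during the cataract surgery (who are unmasked) will be instructed not to discuss the OVD treatment assignment". It describes the masked examiners' task as postoperative measurements.

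On what the Investigator sees, Appendix C says: "The appropriate OVD treatment will be prepared for surgery according to the relevant DFU and made available to the Investigator". It adds: "The Investigator immediately at the end of each surgery will answer the following questions in writing on a subject-specific source document". Under Section 10.5 the two products "will be provided in 1.0 ml and 0.75 ml syringes, respectively".

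The Synopsis names AEs, alongside IOP and intraocular inflammation, as a means of evaluating safety.

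**The concern.** The design promises masked assessment after surgery, but the part of the safety data that depends most on opinion goes to someone who knows the arm. Relatedness rests on whether there is a reasonable possibility of a link to the device. Section 12.4.1 itself notes that adverse effects may come from the surgical procedure or the implanted lens, so the rater has to divide blame among the OVD, the lens and the surgery. Severity also leaves room, because the Moderate and Severe definitions in Section 12.4.3 depend partly on the kind of treatment given.

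One product is investigational. Section 7.1 describes the other as having more than 20 years of use and an established safety record. If that expectation affects how readily an event is blamed on each product, the ADE rates and severity distributions will differ between arms even when the events do not.

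**Working it through.** No sample size, power or error rate is involved, and the plan states no ADE or SAE rate to reproduce. The check is a side-by-side reading.

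1. **Is the Investigator unmasked?** No sentence says so outright. Three things point to it: the Investigator is absent from the masked list in Section 9.2; that section calls staff present at surgery unmasked; and in Appendix C the Investigator receives the assigned OVD and completes the surgical record. The different syringe volumes in Section 10.5 would make the products distinguishable. Appendix C lets a sub-investigator operate only with the Sponsor's prior approval, so the usual case is an Investigator who operates.

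2. **Do the sections conflict?** Sections 7.1 and 11.1.3 with Appendix A, read together, put postoperative AEs with the masked examiner. Sections 12.4.2 and 12.4.3 put observation, elicitation and rating largely with the Investigator. Section 9.2 is narrower than 7.1 and covers measurements only. The conflict concerns postoperative events; preoperative and intraoperative events lie outside the wording of 7.1.

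3. **Which elements are exposed?**
   - Relatedness (AE versus ADE): exposed. It is a judgement with a low threshold.
   - Severity: exposed, for the reason given under the concern.
   - Detection: partly exposed. Section 12.4.2 also lists subject reports and test results; subjects are masked and postoperative measurements are made by masked examiners.
   - Seriousness: less exposed. Death, hospitalization and most other criteria in Section 12.4.1 are fairly objective. The criterion of intervention to prevent permanent impairment leaves the most room.
   - Primary and secondary endpoints (Sections 13.1 and 13.2.2): not exposed by this route. IOP is a tonometry reading and ECD comes from a masked reading center; neither uses the AE rating.

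4. **Is there a second look?** Under Table 3, non-serious events go only onto the AE CRF, and no review of the relatedness call is described. Table 4 shows a Sponsor evaluation in the UADE pathway. Section 13.4.4 has the Sponsor review intraoperative complications masked before lock, but only to define the Best Case Population. The plan thus already uses this safeguard, though not for AEs.

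5. **How large could the bias be?** With the same true AE rate in both arms, the spurious difference in ADE rates is the AE rate × (probability of calling an event related in one arm − the same probability in the other). The documents give no attribution probabilities and no overall AE rate, so no value can be computed.

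**The case against.** The best case for the plan is that Section 9.2, which defines the masked role, speaks of measurements. The Adverse Events row in Appendix A is also marked at the preoperative and operative visits, and its footnote describes a collection period. On that reading Section 7.1 is loosely worded, and Section 12.4.3 properly leaves medical judgement to the Investigator. In addition, SAEs and UADEs reach a largely masked Sponsor within 48 hours, and under Section 9.3.4 any IOP of 30 mmHg or more is notified immediately. AE and ADE rates are not endpoints, and Section 13.5 plans no between-arm AE test.

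Most of this stands and limits the scope. It does not show who rates severity and relatedness of non-serious events without knowing the arm.

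A reader might infer more than the documents support:

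- *That SAE rates are as exposed as ADE rates.* The mostly objective seriousness criteria argue against this.
- *That the trial's safety conclusion is biased.* The tested safety comparisons use measured IOP; the harm falls on descriptive AE reporting.
- *That the bias can be sized.* Taking the planned spike rate of 11.7% and 184 eyes per arm gives 0.117 × 184 = 21.5 spikes. If 80% were called related in one arm and 50% in the other, ADE rates would be 0.117 × 0.80 = 9.4% and 0.117 × 0.50 = 5.9%, a gap of 3.5 points. The 80% and 50% have no basis in the documents, and for spikes the false gap would sit beside an equal measured spike rate in the primary endpoint.
- *That no later step could correct it.* Section 13 defers further detail to an SAP, so one can say only that the text in hand describes no such step.

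**Conclusion.** The point holds with limited reach. The sections disagree on who assesses postoperative AEs, and as written, severity and AE-versus-ADE classification by arm are open to rater bias. This rests on the inference that the Investigator is normally the operating surgeon and so knows the product used. The direction and size of any bias are unknown. It is a cheap improvement to a named safety criterion, not a threat to the primary or secondary conclusions.

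**What to change.** Reconcile Sections 7.1, 9.2, 12.4.2 and 12.4.3 as follows.

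- At postoperative visits the masked examiner asks about AEs and records severity.
- Before database lock, masked Sponsor or medical-monitor staff review relatedness without arm information, on the model of Section 13.4.4. Section 12.4.6 mentions a medical monitor but does not say whether that person is masked or on the Sponsor's side, so this must be confirmed. Reviewers will need the relevant surgical details with product identity withheld.
- All-causality AE rates are the main between-arm AE comparison. The masked relatedness call supports it, and the Investigator's own call is listed alongside.
- Patient care, intraoperative events and expedited reporting stay with the Investigator.

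The cost is protocol wording, extra AE form fields and some masked-review time. Section 9.2 already asks for at least two masked examiners per site, so no added examiner post is foreseen, but their qualifications are not stated and suitability for grading severity should be checked. Intraoperative events would still be rated unmasked.

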12.4.4 Reporting

Actions required by Investigators for reporting non-serious ocular adverse events in the study eye(s) are summarized in **Table 3** below:

Table 3. Non-serious Adverse Events

Adverse Events	Non-device-related	Device-related
Non-serious, ocular, in study eye(s)	AE	ADE
Required Action	Recorded on AE CRFs only. No report to IRB. No expedited report to Sponsor.	

Actions required by Investigators for reporting all serious adverse events in the study eye(s) and/or non-study eye are summarized in **Table 4** below:

[figure not shown]
Table 4. Serious Adverse Events

Serious Adverse Events	Non-device-related	Device-related	
		Anticipated	Unanticipated
Serious, ocular, and non-ocular, in study eye(s) and/or fellow eye	SAE	UADE	
Required Action	Recorded on AE CRF and SAE/UADE Report Form ↓ Investigator provides expedited report to Sponsor and its representative within 48 hours . Report to IRB per IRB policy.	Recorded on AE CRF and SAE/UADE Report Form ↓ Investigator provides expedited report to Sponsor and its representative within 48 hours. Investigator reports to IRB within 10 working days or per IRB policy, whichever is shorter. . Sponsor Conducts Evaluation ↓ Sponsor and its representative & reports to FDA, all IRBs & all Investigators within 10 working days.	

12.4.4.1 On-Site SAE/UADE Reporting

The site must report any adverse event to the Sponsor and its representative in an expedited manner if it meets the criteria for a SAE or a UADE. When reporting a SAE/UADE to the Sponsor and its representative, the site must forward any supporting documents along with the completed UADE Report Form to the Sponsor and its designee within 48 hours of becoming aware of such an event.

The contacts for reporting SAEs/UADEs are:

Sites must also report UADEs to the reviewing IRB per its established reporting procedures or within 10 working days following awareness of the event; whichever is shorter. The site should also complete applicable CRFs within three working days of event identification. The Sponsor or their designee will report the UADE to the FDA within 10 working days after being first informed by the Investigator.

Non-Device related SAEs should also be recorded in the applicable CRFs and submitted to the IRB per IRB policy.

12.4.4.2 Off-Site UADE Reporting

When participating in multicenter clinical investigations, Principal Investigators may receive UADE reports from other participating sites as applicable. These are Sponsor reports of UADEs which occurred at other sites for the same trial, or in different trials using the same test article, that met the criteria for reporting to a regulatory agency. These should be reported to the reviewing IRB per their established reporting procedures or within 10 working days; whichever is shorter.

[figure not shown]
